PROTOCOL: A Prospective, Multi-Center Evaluation of Corneal Flap Creation Using Cheetah Femtosecond Laser System and Cheetah Patient Interface.

Protocol Number: CHTA-103-FLAP

STUDY TREATMENTS: Investigational Product:

1) Cheetah system

2) Cheetah Patient Interface (one or two piece)

Control Product:

1) IntraLase FS

2) Cheetah system with [REDACTED] PI

STUDY OBJECTIVE: This is a [REDACTED] prospective clinical trial to clinically optimize the Cheetah femtosecond laser settings for flap creation [REDACTED] and evaluate the flap quality of the Cheetah system [REDACTED]

[REDACTED]
[REDACTED]
[REDACTED]
[REDACTED]
[REDACTED]

OVERALL STUDY DESIGN:

[figure not shown]
Structure: Prospective, randomized (ratio of 1:1 for right eye and left eye, [REDACTED] multicenter, interventional study.

Number of sites: Up to 5 sites

[REDACTED]
[REDACTED]
[REDACTED]
[REDACTED]
[REDACTED]

STUDY POPULATION CHARACTERISTICS:

Number of Subjects: Up to 30 treated subjects in phase I. In Phase II, a minimum of 40 eyes treated with optimized Cheetah settings are needed. Up to 300 subjects may be treated in both eyes (one study eye, and one control) to achieve the minimum 40 eyes with optimized settings and additional eye data for further device experience.

**Inclusion Criteria [REDACTED] (all criteria apply to both eyes):**

[figure not shown]
- Age \geq 18 years old.
- Subjects with myopia or hyperopia with or without astigmatism (including mixed astigmatism) eligible for commercial LASIK treatment.
- A residual anticipated stromal bed thickness of at least 250 microns based on preoperative central corneal pachymetry minus the maximum treatment depth to be ablated plus the intended flap thickness.
- Distance Best Spectacle Corrected Visual Acuity (BSCVA) of 20/20 or better
- Distance Uncorrected Visual Acuity (UCVA) of 20/32 or worse
- Signed informed consent and HIPAA authorization or equivalent documentation necessary to comply with applicable privacy laws pertaining to medical treatment.
- Willing and capable of complying with follow-up examinations for the duration of the study

[figure not shown]
Exclusion Criteria [REDACTED] (all criteria apply to both eyes):

- Concurrent use of systemic (including inhaled) medications that may impair healing, including but not limited to: antimetabolites, isotretinoin (Accutane[®]) within 6 months of treatment, and amiodarone hydrochloride (Cordarone[®]) within 12 months of treatment.
 - **NOTE: The use of inhaled or systemic corticosteroids, whether chronic or acute, is deemed to adversely affect healing and subjects using such medications are specifically excluded from eligibility.**
- History of any of the following medical conditions, or any other condition that could affect wound healing: collagen vascular disease, autoimmune disease,

[figure not shown]
immunodeficiency diseases, ocular herpes zoster or herpes simplex, endocrine disorders (including, but not limited to unstable thyroid disorders and diabetes), lupus, and rheumatoid arthritis.

- **NOTE: The presence of diabetes (either type 1 or 2), regardless of disease duration, severity, or control, will specifically exclude subjects from eligibility.**
- Subjects with a cardiac pacemaker, implanted defibrillator or other implanted electronic device.
- History of prior intraocular or corneal surgery (including cataract extraction), active ophthalmic disease or abnormality (including, but not limited to, symptomatic blepharitis/conjunctivitis, recurrent corneal erosion, dry eye syndrome, neovascularization > 1 mm from limbus), retinal detachment/repair, clinically significant lens opacity, clinical evidence of trauma, corneal opacity within the central 9 mm and visible on topography, at risk for developing strabismus, or with evidence of glaucoma or propensity for narrow angle glaucoma.
 - **NOTE: Subjects with open angle glaucoma, regardless of medication regimen or control, or an IOP greater than 21 mmHg at screening, are specifically excluded from eligibility.**
- Evidence of keratoconus, corneal dystrophy or irregularity, corneal edema, corneal lesion, hypotony, or abnormal topography.
- Known sensitivity or inappropriate responsiveness to any of the medications used in the postoperative course.
- A fellow eye that does not meet all inclusion criteria and does not fall within approved indications for treatment using excimer Laser.
- Desire for monovision correction
- Women who are pregnant, breast-feeding, or intend to become pregnant during the study.
- Participation in any other clinical study, with the exception of a fellow eye treated in this protocol.

**DATA ANALYSIS:**

[figure not shown]
the key evaluation stromal bed surface quality, using the investigational vs control product. The analysis population will include both eyes of all treated subjects and will be used for all end points. An interim database lock may be performed after approximately 40 subjects have been treated with optimized settings and reached the 1-month postoperative follow-up.

A large rectangular area of the page has been completely blacked out, indicating redacted content.

1. BACKGROUND/INTRODUCTION

JJSV's current femtosecond laser platform is the IntraLase iFS. It creates flaps through precise individual microphotodisruptions of corneal tissue created by tightly focused ultrashort pulses which are delivered through a disposable applanation lens while fixating the eye under vacuum.

[figure not shown]
The Cheetah system is a new femtosecond laser developed by JJSV for the same clinical purpose as the IntraLase iFS system. Similar to the IntraLase iFS, it is used in conjunction with a sterile disposable patient interface (PI), that serves as a physical connection between a patient's eye and the system to facilitate accurate laser incisions to the patient's cornea.

[figure not shown]

The design objective was to develop a flap maker that will be equivalent or better compared to the commercial products. In this study the flap quality and workflow of the study eye will be compared to the control product.

2. CLINICAL HYPOTHESIS

The hypothesis is that the flap quality of the study eye will be equivalent or better than the control eye.

4. ACRONYMS

The following acronyms are used throughout the document:

- D: Diopters
- BSCVA: Best Spectacle Corrected Visual Acuity
- UCVA: Uncorrected Visual Acuity
- MRSE: Manifest Refractive Spherical Equivalent
- OBL: Opaque Bubble Layer
- PI: Patient Interface
- OCT: Optical Coherence Tomography
- QID: 4 times a day (in Latin – quarter in die)

5. STUDY OBJECTIVES AND ENDPOINTS

The purpose of this prospective clinical trial is to [REDACTED] evaluate the flap quality of the Cheetah femtosecond laser [REDACTED]

[REDACTED]
[REDACTED]
[REDACTED]
[REDACTED]
[REDACTED]
[REDACTED]

5.1 PRIMARY STUDY ENDPOINTS

[REDACTED] stromal bed surface quality, [REDACTED] of the study eye will be graded on a scale of 1-5 relative to the control eye. A score of 3 means that the study eye is similar to the control eye; a score of 4 or 5 means that the study eye is superior to the control eye; and a score of 1 or 2 means that the control eye is superior to the study eye. 90% of all subjects are expected to have a score equal to or greater than 3 [REDACTED].

5.2 OTHER ENDPOINTS

- [REDACTED]

- Optical Coherence Tomography (OCT) measurements – Anterior OCT scans will be taken pre- and post-surgery and measurements of the cornea and flap thickness will be recorded.
- BSCVA – Percent of eyes with a loss of >2 lines of best spectacle corrected visual acuity relative to preoperative acuity will be compared between the 2 eyes.
- UCVA – Percent of eyes with uncorrected visual acuity of 20/40, 20/32, 20/25, 20/20, and 20/16 or better will be compared between the 2 eyes.

- [REDACTED]
- [REDACTED]
- [REDACTED]
- [REDACTED]

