7.1 INCLUSION CRITERIA

- [REDACTED]

Inclusion Criteria [REDACTED] (all criteria apply to both eyes):

- 1) Age \geq 18 years old.
- 2) Subjects with myopia or hyperopia with or without astigmatism (including mixed astigmatism) eligible for commercial LASIK treatment.
- 3) A residual anticipated stromal bed thickness of at least 250 microns based on preoperative central corneal pachymetry minus the maximum treatment depth to be ablated plus the intended flap thickness.
- 4) Distance Best Spectacle Corrected Visual Acuity (BSCVA) of 20/20 or better
- 5) Distance Uncorrected Visual Acuity (UCVA) of 20/32 or worse
- 6) Signed informed consent and HIPAA authorization or equivalent documentation necessary to comply with applicable privacy laws pertaining to medical treatment.
- 7) Willing and capable of complying with follow-up examinations for the duration of the study

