10. ADVERSE EVENTS AND PRODUCT COMPLAINTS

10.1 ADVERSE EVENT DEFINITIONS

Adverse Event (AE)

An adverse event is defined (following ISO 14155) as any untoward medical occurrence, unintended disease or injury, or untoward clinical signs (including abnormal laboratory findings) in subjects, users or other persons, whether or not related to the study device.

Serious Adverse Event (SAE)

An adverse event is considered serious (following ISO 14155) if it is an untoward occurrence which may or may not be related to use of the study device that

- is sight- or life-threatening,
- results in death,
- requires inpatient hospitalization or prolongation of hospitalization (a planned hospitalization for a pre-existing condition without a serious deterioration in health is not considered a serious adverse event),
- results in permanent impairment of a body structure or body function,
- necessitates medical or surgical intervention to prevent permanent impairment to a body structure or function, or
- results in fetal distress, fetal death or a congenital abnormality or birth defect

Device-Related Adverse Event/Adverse Device Effect (ADE)

A device-related adverse event is defined as any adverse even that is believed to be definitely, probably or possibly related to the study device (following the guidelines in Section 11.4, Causal Relationship). A device-related event is also considered an adverse device effect (ADE; following ISO 14155) resulting from the use of the study device that may result from user error, insufficiencies or inadequacies in the instructions for use, deployment, implantation, installation, operation of any malfunction of the device.

Study-Specific Anticipated Adverse Events

The following is a list including, but not limited to, ocular adverse events that are anticipated and must be reported to JJSV for this study. Any events that are unlikely but anticipated (i.e., endophthalmitis) will be reported to the FDA and other appropriate regulatory agencies.

- Diffuse lamellar keratitis (DLK) (Grade 3 or above)
- Pressure Induced Stromal Keratitis (PISK)
- Corneal infiltrate or ulcer
- Corneal epithelial defects upon flap creation
- Any persistent corneal epithelial defect at 1 month or later
- Corneal edema at 1 month or later
- Epithelium in the interface with loss of 2 or more lines of BSCVA (≥ 10 ETDRS letters)
- Miscreated flap (decentered, lost, incomplete, too thin or other)
- Melting of the flap

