- IOP with increase > 10 mmHg above baseline on two consecutive examinations or an IOP greater than 30 mmHg on two consecutive examinations
- Haze at 3 months or later with loss of 2 or more lines of BSCVA (≥ 10 ETDRS letters)
- Interface haze
- Decrease in BSCVA of 2 or more lines (≥ 10 ETDRS letters) not due to irregular astigmatism as shown by hard contact lens refraction (or pin hole acuity if hard contact lens refraction is not medically advisable) at 3 months or later
- Retinal detachment
- Retinal vascular accidents
- Any other vision-threatening event
- Ocular penetration
- Rainbow glare
- Severe glare, severe dry eye, or severe halos at 3 months or later

[REDACTED]

[REDACTED]

[REDACTED]

[REDACTED]

[REDACTED]

[REDACTED]

[REDACTED]

[REDACTED]

Unanticipated Adverse Device Effect (UADE)/Unanticipated Serious Adverse Device Effect (USADE)

Any UADE (USA 21CFR 812.3(s)) or USADE (ISO 14155) is defined as any serious adverse effect on health or safety or any life-threatening problem or death caused by, or associated with, a device, if that effect, problem, or death was not previously identified in nature, severity, or degree of incidence in the investigational plan (i.e., this protocol), application (including a supplementary plan or application), or risk assessment, or any other unanticipated serious problem associated with a device that relates to the rights, safety, or welfare of subjects.

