10.3 ADVERSE EVENT AND COMPLAINT REPORTING REQUIREMENTS

All adverse events and any complaint encountered using any JJSV product, regardless of severity and whether or not attributed to the study device(s), are to be reported to JJSV and recorded on the case report form corresponding to the visit during which awareness of the event occurred. Adverse events are also to be reported to the reviewing IRB/IEC as per the IRB/IEC's reporting requirements. If required, adverse events will be reported to the appropriate regulatory agencies (e.g., FDA) according to all applicable laws and regulations. Specific instructions on notification procedures to JJSV are included in **Appendix K**, Adverse Event Reporting.

Reporting of adverse events shall follow the USA Code of Federal Regulations (21CFR812) for sites in the USA. For sites located outside the USA, reporting of adverse events shall follow ISO 14155 and country-specific guidelines, of which the

shortest/strictest timeline requirement for reporting adverse events will be followed. General guidelines are provided below:

Adverse Event Reporting

An adverse event that is not serious or device-related is to be reported to JJSV in a timely manner. Notification of non-serious and non-device related adverse events will occur by recording events on the CRF when noted. Such adverse events are also to be reported to the reviewing IRB/IEC per their reporting requirements.

Complaints/Device Deficiency Reporting

A general product complaint or device deficiency is to be reported to JJSV in a timely manner. Notification of complaints/device deficiencies will occur by either recording complaints on the CRF when the complaint occurred (e.g. operative form) or by a phone call to the Sponsor. Any device deficiency that could have led to a serious adverse event without suitable action or intervention, or under less fortunate circumstances, must be reported to the sponsor immediately (no later than 48 hours after detection). Device deficiencies that could have led to a serious adverse event should also be reported to the investigator's IRB/IEC per their reporting requirements.

Serious and/or Device-Related Adverse Event Reporting

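### Should the between-eye comparison of BSCVA loss use the same cut-off (2 or more lines) as the adverse event list?

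*Protocol*

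**What the plan says.** Protocol 5.2 (Other Endpoints) has one visible bullet on best-corrected acuity. It compares the two eyes on "Percent of eyes with a loss of >2 lines of best spectacle corrected visual acuity relative to preoperative acuity".

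Protocol 10.1 (Adverse Event Definitions) has three visible items that involve a loss of best-corrected acuity:

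- "Epithelium in the interface with loss of 2 or more lines of BSCVA (≥ 10 ETDRS letters"), with no time limit;
- "Haze at 3 months or later with loss of 2 or more lines of BSCVA (≥ 10 ETDRS letters");
- "Decrease in BSCVA of 2 or more lines (≥ 10 ETDRS letters) not due to irregular astigmatism", which applies at 3 months or later.

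The list is introduced as not exhaustive, and it also contains a general item for any other event that threatens vision. Protocol 10.3 requires reporting of "All adverse events and any complaint encountered using any JJSV product, regardless of severity".

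Protocol 7.1 sets the entry level: "Distance Best Spectacle Corrected Visual Acuity (BSCVA) of 20/20 or better". Protocol 19.3 and SAP 5.2 visibly promise summaries of adverse events by type and as rates. Five other bullets of Protocol 5.2, most of Protocol 19.3 and nearly all of SAP 5.2 are redacted.

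**The concern.** The same protocol uses two cut-offs for the same measurement, one strict and one inclusive, and the visible text does not explain the difference. Read side by side, they suggest a drafting slip.

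The gap can be made concrete. An eye that enters at 20/20 and ends at a best-corrected 20/32 has lost exactly 2 lines on the acuity steps that 5.2 uses for uncorrected acuity ("Percent of eyes with uncorrected visual acuity of 20/40, 20/32, 20/25, 20/20, and 20/16 or better"). That eye is not counted in the 5.2 percentage. Nor does it meet any of the three adverse event items unless it has interface epithelium, or has haze at 3 months or later, or has a loss at 3 months or later that is not due to irregular astigmatism.

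Timing appears to sharpen the point, because the synopsis says: "An interim database lock may be performed after approximately 40 subjects have been treated with optimized settings and reached the 1-month postoperative follow-up". For subjects not yet at 3 months, only the interface-epithelium item of the three could apply. At stake would be a between-eye safety comparison that misses moderate acuity losses.

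**Working it through.** **1. Inputs.** Protocol 10.1 equates 2 lines with 10 letters, so one line is 10/2 = 5 letters. All three items use this equivalence consistently. The documents give no event rate, SD, sample size or power for acuity loss, so there is no stated figure to reproduce.

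**2. Which eyes fall between the cut-offs.** The step from 20/20 to 20/25 is log10(25/20) = 0.097, and from 20/20 to 20/32 it is log10(32/20) = 0.204. The second is therefore two steps of about 0.10 logMAR. At 0.02 logMAR per letter, a 10-letter loss from 20/20 gives 20 × 10^0.20 = 31.7, that is 20/32, which is not counted. An 11-letter loss gives 20 × 10^0.22 = 33.2, which is counted. With letter scoring the gap is exactly 10 letters. With whole-line scoring, more than 2 lines means 15 or more letters, and the gap is 10 to 14 letters.

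**3. Whether the two rules must agree.**

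| | Protocol 5.2 bullet | Protocol 10.1 items |
|---|---|---|
| Purpose | percentage per eye, compared between eyes | trigger for reporting an event |
| Conditions | none beyond the loss itself | interface epithelium; haze at 3 months or later; or not due to irregular astigmatism at 3 months or later |
| Complete list? | one visible bullet, five others redacted | expressly open-ended |
| Same rule for both eyes? | yes | yes |

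Nothing in either section says that one is to be derived from the other. Followed as written, 5.2 gives a well-defined count that treats both eyes alike. Leaving out exact 2-line losses lowers the reported rate under the same rule in each eye, so the rule itself does not favour one eye.

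**4. Whether the eye is lost to safety reporting.** It is not. The general rule in 10.3 covers adverse events of any severity, and the 10.1 list does not limit it. This holds before 3 months as well as after. The synopsis says only that an interim lock may take place, and it names stromal bed surface quality as the key evaluation. No visible text says that acuity loss is analysed at that lock.

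**5. Possible size.** Everything here rests on an assumption: letter change is Normal with mean 0 and the SD shown. With a continuity correction, P(10 or more) = 1 − Φ(9.5/SD), P(11 or more) = 1 − Φ(10.5/SD), and d is the difference.

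| Assumed SD (letters) | P(10 or more) | P(11 or more) | d | 40 × d | 1 − (1 − d)^40 |
|---|---|---|---|---|---|
| 3 | 0.0008 | 0.0002 | 0.0005 | 0.02 | 0.02 |
| 4 | 0.0088 | 0.0043 | 0.0044 | 0.18 | 0.16 |
| 5 | 0.0287 | 0.0179 | 0.0109 | 0.43 | 0.35 |
| 6 | 0.0567 | 0.0401 | 0.0166 | 0.66 | 0.49 |
| 8 | 0.1175 | 0.0947 | 0.0228 | 0.91 | 0.60 |

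The 40 is the synopsis minimum of eyes treated with optimized settings. With whole-line scoring at SD 5, P(15 or more) = 0.0019, and the gap is 40 × (0.0287 − 0.0019) = 1.07 eyes instead of 0.43. The result moves with the assumed SD and the scoring rule, neither of which the visible text supplies. The top of the range is also implausible: at SD 8 a symmetric model has 11.75% of eyes gaining 10 or more letters, although every eye enters at 20/20 or better.

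**The case for a change.** The best case for the concern is that the trial is built on paired eyes and that the 5.2 bullet is the only visible place where acuity loss is set out eye against eye. Adverse events are visibly summarized by type and as rates, with no visible split by eye. A 10-letter loss reported as an adverse event would thus be on record but, on the visible text, not in a study-versus-control comparison. If lines are scored whole, most losses of 10 or more letters would fall outside the endpoint: between 86% (SD 6) and 98% (SD 4) under the same assumed model. A further row would cost little, since ETDRS score cards are already source documents under Protocol 13.1.

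Part of this stands. The quotations are accurate, the cut-offs do differ, and 5.2 does not say how its lines convert to letters. An added row would be a reasonable courtesy to the reader. But a table that one would like to see is not an error in the table that is planned. Nor can the missing row be asserted: the redacted bullets of 5.2 and the redacted parts of Protocol 19.3 and SAP 5.2 are where such a row, or a by-eye adverse event table, would appear. Text withheld by redaction does not count as absent from the plan. The low cost is also partly inferred, because 13.1 has the sites retain the score cards but does not say that letter scores are entered in the study database.

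**Conclusion.** The concern does not hold. The endpoint in Protocol 5.2 and the event definitions in 10.1 use different cut-offs for different purposes, and neither makes the other wrong. The 5.2 comparison is valid as written, identical for both eyes and non-primary, with no visible test, margin or power. The primary endpoint and the planned numbers are untouched, and exact 2-line losses remain reportable as adverse events.

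The size of the gap cannot be derived from the documents. With letter scoring and an assumed SD of 4 to 8 letters it is about 0.2 to 0.9 of 40 study eyes. It is 0.02 at SD 3 and larger if lines are scored whole. The conclusion does not depend on these figures. It rests on taking the printed strict inequality in 5.2 at face value, on the different roles of the two sections, and on not treating redacted text as missing.

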6. STUDY PRODUCTS

6.1 CHEETAH SYSTEM

The Cheetah system (Models Beta 2a, [Figure 1](#); or Production Equivalent (ELITA), [Figure 2](#) is an ophthalmic laser surgical system that is developed for use in the creation of a corneal flap in patients undergoing LASIK surgery or other treatment requiring initial resection of the cornea. Either model can be used in this study.

Figure 1. Cheetah Beta2a Femtosecond Laser system

Figure 2. Production Equivalent (ELITA) Femtosecond Laser System

The Cheetah System is an investigational device. It is approved in the EU and UK, but is not yet approved in the U.S.A. The Principal Investigator is responsible for ensuring that the Cheetah system is only used to treat subjects enrolled in this study.

6.2 CHEETAH PATIENT INTERFACE

The Patient Interface (PI) is an accessory to the Cheetah System. The PI serves as a physical connection between a patient's eye and the system to facilitate accurate laser incisions to the patient's cornea.

The two piece patient Interface consists of the PI cone that contains the applanation lens and attaches to the system and the PI suction ring which has vacuum line to the system [REDACTED] The PI cone has a protective cap to assist in connecting it to the system while keeping the applanation lens free from fingerprints and contaminants. During docking, the PI cone is attached to the PI mount of the Cheetah system and the PI suction ring is attached to the patient's eye. The PI cone is lowered toward the patient's eye and mechanically attaches to the PI suction ring. [REDACTED]

[figure not shown]
[figure not shown]

Figure 3. Cheetah Patient Interface components

Figure 4. Cheetah Patient Interface in packaging tray with vacuum line system. The PI cone is packed inside its protective cap

[REDACTED] The two piece Cheetah patient interface is approved in the EU, UK, and U.S.A. The Principal Investigator is responsible for ensuring that the Patient Interface is only used to dock subjects enrolled in this study.

